#### **4.5 MANAGEMENT OF SUBJECTS WHO DO NOT REACH 48 WEEKS IN THE ASSIGNED STUDY ARM**

Subjects who do not reach 48 weeks in their assigned study arm will continue to be followed and will complete all study evaluations of the final visit. They will be treated in the analysis as detailed in Section 11.0.

### **5 SELECTION AND ENROLLMENT OF SUBJECTS**

#### **5.1 STEP 1**

##### **5.1.1 Description of Population**

Step 1 will screen MSM and transgender women, unaware of their HIV status and with evidence of high risk for acquiring HIV-1 infection, including sexual risk behavior, partner of a newly-diagnosed person with acute or recent HIV infection, or with symptoms of acute retroviral syndrome. These men will have voluntarily visited one of our collaborating testing centers in Lima. We will also attempt to increase voluntary testing to help with our recruitment by using educational campaigns on acute HIV symptoms, community mobilization for increased frequency of testing, advertisements on radio, and recruitment of prior study participants, many

of whom in active contact with EPICENTRO, VIA LIBRE and IMPACTA (with its two clinics: San Miguel and Barranco).

### **5.1.2 Inclusion Criteria**

Individuals will be included in the study if they meet ALL of the following criteria:

1. Male sex (at birth);
2. Eighteen years of age or older;
3. Unaware of their HIV status;
4. Ability and willingness to provide informed consent for study participation, including being tested for HIV-1; for re-testing if HIV negative (Step 2); and to consider enrollment in an immediate vs. deferred ART trial (Step 3) if diagnosed with acute or recent HIV infection after testing. People diagnosed with HIV infection during participation in Step 2 will be offered enrollment in Step 3.
5. Willingness to be re-contacted if HIV seronegative by antibody analysis but with virologic evidence of acute infection HIV-1 and to be linked to care;
6. Evidence of high risk for acquiring HIV-1 infection, including any one of the following:
  - a. Sexual behaviors:
    - i. Inconsistent condom use during anal intercourse during the last 6 months;
    - ii. Anal intercourse with more than 5 male sex partners during the last 6 months;
    - iii. Self-identification as a sex worker;
    - iv. STI diagnosis during the last 6 months or at screening; or
    - v. Sexual partner of an HIV-infected man in the last 6 months.
  - b. Partner of a newly-diagnosed person with acute or recent HIV infection;
  - c. Someone seeking HIV testing because of symptoms of acute retroviral syndrome;
7. Able to provide contact information, including (1) one or more phone numbers (cell and/or home) and/or a street address of residence for themselves and (2) personal contact information (ideally from two or more people) who would know their whereabouts during the study period.

---

 The "1" refers to the footnote which describes the following "Feibig stage 1 (presence of HIV RNA only) or Feibig Stage 2 (presence of HIV RNA and antigen p24)

8. Ambulatory performance status  $\geq 80$  on the Karnofsky scale.

### **5.1.3 Exclusion Criteria**

1. Any medical, psychological/psychiatric, occupational, or other condition that, in the judgment of the investigator, would interfere with, or serve as a contraindication to, protocol adherence, assessment of safety, or a participant's ability to give informed consent;
2. Seeking HIV test behavior for routine reasons.
3. Use of estrogens (or its derivatives) or anti-androgens, administered orally or intra-muscularly, during the past three months.

## **5.2 STEP 2**

In Step 2, high-risk MSM and transgender women with no HIV-1 infection identified in Step 1 will be asked to repeat testing every 3 months for incident HIV-1 infection while receiving standard risk reduction counseling, condoms, and management of STIs.

### **5.2.1 Inclusion Criterion**

Individuals will be asked to participate in repeat testing if they are found to be HIV-negative in Step 1.

### **5.2.2 Exclusion Criterion**

Any medical, psychological/psychiatric, occupational, or other condition that, in the judgment of the investigator, would interfere with, or serve as a contraindication to, protocol adherence, assessment of safety, or a participant's ability to give informed consent;

## **5.3 STEP 3**

### **5.3.1 Description of Population**

Step 3 will be conducted among high-risk MSM and transgender women with acute or recent HIV infection during their participation in Step 1 or Step 2 willing to be randomized to immediate vs. deferred ART, unless ART criteria are met earlier.

### **5.3.2 Inclusion Criteria**

1. Determination of acute or recent HIV infection (either in Step 1 or Step 2), as defined by the HIV test algorithm described in Section 7.1. (Also see Appendix 1 for Study Flow Diagram and Appendix 2 for HIV categories by test results).

---

 This case definition fulfills the definition of World Health Organization (WHO). According to the WHO, HIV case definition among adults and children 18 months or older is as follow:

- Positive HIV antibody testing (rapid or laboratory-based enzyme immunoassay). This is confirmed by a second HIV antibody test (rapid or laboratory-based enzyme immunoassay) relying on different antigens or of different operating characteristics;

a. Acute HIV infection:

Third-generation HIV test negative (HIV antibody negative), HIV-1 RNA test positive, and a confirmatory HIV test positive;

b. Recent HIV infection:

Third-generation HIV test positive (HIV antibody positive), HIV negative test in Step 2 in the previous 3 months, and a confirmatory HIV positive test.

Individuals who have been diagnosed with HIV in any health clinic or laboratory authorized by the Ministry of Health, and that have had a documented negative result in the past three months can also participate in Step 3.

2. No prior ART, including prior administration of pre- and post-exposure prophylaxis in the last 30 days of HIV diagnosis;
3. Laboratory values obtained within 28 days prior to study entry:
  - a. AST (SGOT) and ALT (SGPT)  $\leq 5 \times$  ULN;
  - b. Serum phosphorus  $> 2.0 \text{mg/dl}$
  - c. Serum creatinine  $< 1.4 \times$  ULN,
  - d. Calculated creatinine clearance (CrCl)  $> 70 \text{mL/min}$  (Cockcroft-Gault formula);
  - e. Serum lipase  $\leq 1.5 \times$  ULN.

4. Ability and willingness to provide written informed consent for being screened and if qualifying, to be randomized to immediate vs. deferred ART, to remain in their assigned arm and then, continue ART from other sources.

### **5.3.3 Exclusion Criteria**

1. Presentation with WHO clinical stage 3 or 4 irrespective of CD4 count.
2. Use within 21 days prior to study entry of drugs that are highly dependent on CYP3A for clearance and for which elevated plasma concentrations are associated with life-threatening adverse events or drugs that strongly induce CYP3A and lead to lower exposure of one or more components and loss of efficacy of STRIBILD and possible resistance: alfuzosin, astemizole, cisapride, ergot alkaloids and derivatives, flecainide, St. John's wort, lovastatin, simvastatin, triazolam, oral midazolam, pimozide, propafenone, rifampin, simvastatin, sildenafil, terfenadine, and fluticasone-containing

---

*and/or*

- Positive virological test for HIV or its components (HIV-RNA or HIV-DNA or ultrasensitive HIV p24 antigen) confirmed by a second virological test obtained from a separate determination.

compounds.. Check the most recent co-formulated elvitegravir/cobicistat/emtricitabine/tenofovir disoproxil fumarate (STRIBILD®) or co-formulated emtricitabine/tenofovir DF/efavirenz package inserts for other exclusionary medications. Estimated creatinine clearance below 70 mL per minute

3.

Prior receipt of investigational anti-HIV vaccine.

4. Ongoing therapy with any of the following:

- a. Systemic corticosteroids. Short course less than or equal to 21 days of corticosteroids is allowed;
- b. Systemic chemotherapeutic agents;
- c. Nephrotoxic systemic agents, including aminoglycosides, amphotericin B, cidofovir, cisplatin, foscarnet, pentamidine;
- d. Immunomodulatory treatments including Interleukin-2;
- e. Investigational agents;

5. Known allergy/sensitivity or any hypersensitivity to components of study drugs or their formulations;
6. Active drug or alcohol use or dependence that, in the opinion of the site investigator, would interfere with adherence to study requirements;
7. Serious medical or psychiatric illness that, in the opinion of the site investigator, would interfere with the ability to adhere to study requirements;
8. Chronic (HBsAg positive, anti-HBc positive, Ig M anti-HBc negative, and anti-HBs negative) or acute (HBsAg positive, anti-HBc positive, Ig M anti-HBc positive, and anti-HBs negative) hepatitis B infection.
9. Use of estrogens (or its derivatives) or anti-androgens, administered orally or intramuscularly, during the past three months.

## **6 STUDY TREATMENT**

### **6.1 STEP 1**

No study treatment is offered.

### **6.2 STEP 2**

No study treatment is offered.

### **6.3 STEP 3**

#### **6.3.1 Regimens, Administration, and Duration**

##### **6.3.1.1 Regimen**

Those participants, who have initiated their participation in the study before the approval of **Amendment Letter #1** in this study protocol, will continue their participation as originally programmed.

Once the **Amendment Letter #1** is approved for this study protocol, the participants who are eligible for Step 3 will be given treatment the following way:

- Those people diagnosed with **acute HIV infection** will be offered immediate ART (just at time of the enrollment visit or during the next 48 to 72 hours) for the duration of 48 weeks.

Weeks 0-48: Co-formulated elvitegravir/cobicistat/emtricitabine/tenofovir disoproxil fumarate (or co-formulated emtricitabine/tenofovir DF/efavirenz) orally once daily.

Those people diagnosed with recent HIV infection will be randomized to one of the following arms:

1. Arm 1:

Weeks 0-48: Co-formulated elvitegravir/cobicistat/emtricitabine/tenofovir disoproxil fumarate (or co-formulated emtricitabine/tenofovir DF/efavirenz) orally once daily.

2. Arm 2:

Week 0-24: No treatment unless Peruvian criteria for initiation of treatment are met.

Week 25-48: Co-formulated elvitegravir/cobicistat/emtricitabine/tenofovir disoproxil fumarate (or co-formulated emtricitabine/tenofovir DF/efavirenz) orally once daily.

##### **6.3.1.2 Administration**

Co-formulated elvitegravir/cobicistat/emtricitabine/tenofovir disoproxil fumarate will be administered as one tablet orally once daily with food. Co-formulated emtricitabine/tenofovir DF/efavirenz will be administered as one tablet orally once daily at bedtime with or without food.

##### **6.3.1.3 Duration**

Those participants, who have started their participation in the study before the approval of **Amendment Letter #1** in this study protocol, will continue their participation as originally programmed.

Once the Amendment Letter #1 is approved for this study protocol, the participants who have been diagnosed with **acute HIV infection**, and decide to participate in the study will receive treatment duration of 48 weeks.

For the people who are diagnosed with **recent HIV infection** and decide to participate, treatment will depend on which arm they are assigned to:

Arm 1 will receive study treatment for 48 weeks. Arm 2 will receive no treatment for 24 weeks and then receive 24 weeks of study treatment. However, if during the first 24 weeks of no treatment, clinical, virologic, or immunologic criteria of treatment initiation are met, subject will be offered treatment initiation. ART will be provided by the study for the duration of the time that the participant remains in the study. At the end of study, participants will continue ART from other sources.

### **6.3.2 Product Formulation and Preparation**

Elvitegravir/cobicistat/emtricitabine/tenofovir disoproxil fumarate (STRIBILD®) is co-formulated to contain 150 mg of elvitegravir, 150 mg of cobicistat, 200 mg of emtricitabine, and 300 mg of tenofovir disoproxil fumarate, in each tablet. Emtricitabine/tenofovir DF/efavirenz (Atripla™) is co-formulated to contain 200 mg of emtricitabine, 300 mg of tenofovir DF and 600 mg of efavirenz in each tablet. Each bottle contains a silica gel desiccant canister that should remain in the original container to protect the product from humidity. Dispense in the original container. Store at 25°C (77°F), excursions permitted to 15°-30°C (59°-86°F).

Co-formulated emtricitabine/tenofovir (Truvada™) contains 200 mg of emtricitabine and 300 mg of tenofovir DF in each tablet. Each bottle contains a silica gel desiccant canister that should remain in the original container to protect the product from humidity. Dispense in the original container. Store at 25°C (77°F), excursions permitted to 15°-30°C (59°-86°F).

Efavirenz of 600 mg in each tablet, will be dispensed in blister packs of 10 tablets. Store at 25 °C (77°F), excursions permitted to 15°-30°C (59°-86°F).

### **6.3.3 Product Supply**

Co-formulated elvitegravir/cobicistat/emtricitabine/tenofovir disoproxil fumarate (STRIBILD®) will be provided by Gilead Sciences, Inc while co-formulated emtricitabine/tenofovir DF/efavirenz (Atripla™) will be provided by Merck & Co., Inc., under previous agreement with Gilead Sciences. Co-formulated emtricitabina/tenofovir DF (Truvada™) will be provided by Gilead Sciences. Efavirenz will be purchased locally from commercially available sources.

### **6.3.4 Pharmacy Facilities**

The pharmacy facilities are located at the IMPACTA Barranco and IMPACTA San Miguel Clinical Research Sites and both are staffed by registered trained pharmacists. Both pharmacies will have adequate space to store sufficient quantities of study agent to assure continuous access to all study participants. The study drug will be stored in accordance with the drug manufacturer's recommendations. Both pharmacies' storage and the study pharmacies will be locked by a secure door. The pharmacies and storage facilities have climate-controlled

environments, with controlled humidity and temperature to remain within limits allowed by the manufacturer for drug storage.

### **6.3.5 Drug Inventory**

The pharmacists at the IMPACTA Barranco and IMPACTA San Miguel Clinical Research Sites will receive the study agent and store it in the pharmacy. Access will be restricted to authorized pharmacy personnel only. The pharmacists will be responsible for keeping accurate records of the material received. At the end of the study, the pharmacists will perform the final drug accounting of unused study material on the proper log documents. Unused study agent will be disposed of in accordance with local regulations.

### **6.3.6 Drug Dispensing**

The Study Pharmacist will be responsible for dispensing the drug to the Study Nurse who will deliver it to the participant. At each visit, the pharmacist will receive the prescription that includes the participant's enrollment ID number. The pharmacist will dispense drug according to the randomization procedure below. For bottle dispensed, the pharmacist will enter the packed label information and date in a Drug Dispensation Log, to be kept secure in the Pharmacy.

### **6.3.7 Concomitant Medications**

To avoid adverse events caused by drug interactions, investigators must refer to the most recent package insert for study drug and concomitant agents whenever a concomitant medication is initiated or a dose is changed.

Sites must also refer to the study product's most recent package insert or investigator brochure to access additional current information on prohibited and precautionary medications.

Below are lists of selected concomitant medications. These lists are only current as of the date of this protocol. Therefore, whenever a concomitant medication or study agent is initiated or a dose changed, investigators must review the concomitant medication's and study agent's most recent package inserts or investigator brochure to obtain the most current information on drug interactions, contraindications, and precautions.

#### **6.3.7.1 Precautionary Medications**

Package inserts of antiretroviral drugs and concomitant agents should be referenced whenever a concomitant medication is initiated or a dose is changed to avoid drug interaction AEs.

#### **6.3.7.2 Prohibited Medications**

Co-administration with drugs that are highly dependent on CYP3A for clearance and for which elevated plasma concentrations are associated with serious and/or life-threatening events is contraindicated. These drugs and other contraindicated drugs (which may lead to reduced efficacy of STRIBILD and possible resistance) are listed in the table below.

Drugs that are Contraindicated with STRIBILD

MEDICATION CLASS	PROHIBITED MEDICATIONS
ALPHA 1-ADRENORECEPTOR ANTAGONIST	Alfuzosin
ANTIMYCOBACTERIAL	Rifampin
ERGOT DERIVATIVES	Dihydroergotamine Ergotamine Methylergonovine
GI MOTILITY AGENT HERBAL PRODUCTS	Cisapride St. John's wort ( Hypericum perforatum )
HMG-COA REDUCTASE INHIBITORS	Lovastatin Simvastatin
NEUROLEPTIC	Pimozide
PHOSPHODIESTERASE-5 (PDE5) INHIBITOR	Sildenafil when dosed as REVATIO for the treatment of pulmonary arterial hypertension
SEDATIVE/HYPNOTICS	Triazolam Orally administered midazolam

Drugs that are contraindicated with Atripia

Medication Class	Prohibited Medications*
ANTIHISTAMINES	astemizole (Hismanal) terfenadine (Seldane)
ANTI-INFECTIVES	rifampin (Rifadin, Rimactane)
GASTROINTESTINAL-MOTILITY	cisapride (Propulsid)
HYPOLIPEMICS	lovastatin (Mevacor) simvastatin (Zocor)
PSYCHIATRIC MEDICATIONS	pimozide (Orap) St. John's wort ( Hypericum perforatum )
SEDATIVES	midazolam (Versed)** triazolam (Halcion)
OTHER	alfuzosin (Uroxatral) dexamethasone dihydroergotamine (Migranal, Cafergot) eletriptan (Relpax) ergonovine (Ergotrate, Ergostat) ergotamine (Ergostat, Gotamine, Bellergal) fluticasone containing compounds (e.g., flonase, Flovent, Advair) methylergonovine (Methergine, Wigraine)

\* Some brand names are showed, but attention must be taken about the generic name.

\*\*A single dose of midazolam may be used for sedation in subjects undergoing procedures in a monitored setting.

NOTE: Subjects receiving the medications listed above who are randomized to receive immediate or deferred ART during the course of the study must agree to receive an alternative antiretroviral regimen that has been approved by the Protocol Chair.

#### ***6.3.7.3 Options for Medication Substitutions Due to Intolerance/Toxicity***

If intolerance or toxicity occurs, substitutions may be made to the study regimen, after discussion with the Protocol Chair, as long as the new regimen is consistent with current guidelines for potent ART. The substituted medications will be provided by the study for the duration of time that the participant remains in the study. The purpose of the study is to determine whether ART in general, not necessarily this specific regimen, affects the impact of immediate and deferred ART on the decay dynamics of HIV viral load in plasma, semen and rectal secretions of individuals with acute or recent infection.

#### ***6.3.7.4 Options for Medication Substitutions for Virologic Failure***

If a subject develops virologic failure on the study regimen further management based in clinical judgment should proceed at the discretion of the On-Site Principal Investigator in consultation with the Protocol Chair. .

Substitutions in antiretroviral regimens during the course of the study are at the discretion of the site investigator. It is the site investigator's responsibility to review all concomitant medications to ensure safety. The protocol pharmacist is available for discussion if questions arise.

[figure not shown]
The substituted medications will be provided by the study for the duration of time that the participant remains in the study.

#### **6.3.8 Adherence Assessment**

Adherence will be assessed via validated self-report measures, pharmacy refill-based measures, and unexpected increases in HIV plasma viral load. Specifically, the Visual Analogue Scale [171] and the Ability Likert item [172] will be used to collect self-reported adherence over the past 30 days, collected monthly. These measures have demonstrated consistent associations with viral load in other studies [173]. Because self-report has a number of limitations, including a tendency of over-estimate adherence in comparison to electronic drug monitoring measures as well as potentially high demands on other cognitive processes to produce accurate reports [174], we also will monitor pharmacy dispensation records to produce medication possession ratios (days covered by a script/days between scripts) in approximately 3-month intervals. Pharmacy-based measures of adherence have consistently been associated with clinical outcomes in previous research [175, 176]. We will not monitor ART blood levels because a) this is not done as part of routine clinical practice, b) the tests would only refer to recent adherence rather than adherence over time, and c) it is rather expensive to conduct these tests.

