Chemistry/LFT				X		X	X			X							X	
Lipid panel	X***						X			X							X	
Urinalysis	X			X			X			X							X	
Hepatitis B serology																		
STI testing	X						X			X							X	
CD4+/CD8+ cells count	X			X			X			X					X		X	
Plasma HIV-1 RNA	X	X	X	X	X	X	X	X	X	X					X		X	
Semen and rectal secretion collection	X	X	X	X	X	X	X	X	X	X					X		X	
Screening questionnaire - Demographics	X																	
AUDIT	X																	
Interviewer – Monthly questionnaire*	X			X		X	X	X	X				X	X	X	X	X	
Quarterly questionnaire**	X					X			X					X			X	
Pharmacy Refills				X		X	X	X	X				X	X	X	X	X	
Hair Sample	X					X			X					X			X	
Blood volumes (ml) for participants with immediate treatment	160	60	60	71.5	10	121.5	21.5	110	10	121.5	50	50	50	100	13	100	0	121.5
Blood volumes (ml) for participants with deferred treatment	230	60	60	71.5	0	201.5	21.5	190	10	201.5	50	50	50	100	13	100	0	121.5

\*Monthly interviewer-administered questionnaire containing: Timeline Follow Back (alcohol use and sexual behavior), Visual analog scale for ART adherence, and Medication adherence program choices

\*\*Quarterly questionnaire containing: Drug and alcohol use (drug use history, DAST 10, drinking expectancies); Mental health and wellbeing (RAND 12, Social support scale, Stigma scale, Stigma and disclosure, Partner notification, Intimate partner violence, 10 item CES-D, CID Mental health items on anxiety, stress & coping; Medical care (Hospitalization and ER use, Barriers to care, Access to care, Self-efficacy for ART use). \*\*\* These will be done within 72 hours.

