### **7.4.2.5 Premature Treatment Discontinuation Evaluation Provided by the Study**

Subjects who voluntarily discontinue treatment provided by the study will be advised to continue anti-retroviral treatment with public or private sources. The study investigators will take necessary steps to ensure that the subjects continue ART. Counseling will be provided with a special emphasis on safety, and later efficacy options to use in the future if the participant decides to discontinue ART provided by the study and not continue with any other. All the participants will be invited to continue with the follow-up evaluations according to the originally specified "Timing of Visits".

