#### **11.2.2 Secondary Endpoints**

1. To identify associated risk factors for incident HIV-1 infection.
2. To identify sequence clusters using phylogenetic analysis among participants with early HIV infection.
3. To compare self-reported sexual risk behavior, partner characteristics, entertainment venue attendance, and method of referral in MSM and transgender women within clusters to those outside of clusters.

4. To determine the proportion of individuals with evidence of acute infection (HIV-1 RNA-positive) who are successfully contacted for confirmatory HIV testing and are then linked to care.
5. To determine the proportion of newly identified HIV-positive men willing to name at least one recent sexual partner, and the proportion of named partners subsequently contacted and tested.
6. To determine the proportion of men retained in care, including adherence to ART and study procedures, among individuals with early HIV-1 infection receiving immediate and deferred ART.

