#### **11.5.4 Modeling the Expected Intervention Impact at Population Level**

Data for model development will come from several sources. We will use data from the study testing centers to estimate the percentage of total HIV infections detected during AHI and the distribution of testing intervals among MSM and transgender women attending participating VCT centers. We will use results of the formative research to modify the baseline questionnaire compiled by [name] from multiple validated surveys such as the Addiction Severity Index, Brief Symptom Inventory, etc. and use it to collect extensive data from all enrolled participants on sexual risk behaviors, drug and alcohol use, adherence to ART, social support, mental health and psychiatric status. Data will be collected from men with Acute and recent HIV infection (and consenting HIV+ partners) with or without alcohol use disorder. Data on sexual networks will be obtained by partner tracing and phylogenetic analysis. Clinical (CD4+ cell count, HIV viral load)

and adherence data (pill count, recall) will be used for analysis and incorporated into models as appropriate. Data will be managed at the Data Management Center (DMC) at the IMPACTA Barranco Clinical Research site, with experienced staff that participated in multiple NIH-funded studies. The DMC will be responsible for forms development, data entry, database management, adverse event reporting, specimen tracking, report generation, quality control and data security.

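### The refill adherence ratio has no denominator after the last script, so time after a participant stops collecting ART is dropped or undefined and adherence can be overstated

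*Combined protocol and SAP*

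**What the plan says.** Section 6.3.8 names three sources of adherence information: "Adherence will be assessed via validated self-report measures, pharmacy refill-based measures, and unexpected increases in HIV plasma viral load". The refill-based source is "medication possession ratios (days covered by a script/days between scripts) in approximately 3-month intervals". The section adds it because self-report tends to overstate adherence.

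Adherence belongs to secondary endpoint 6 in Section 11.2.2: "To determine the proportion of men retained in care, including adherence to ART and study procedures". The endpoint covers both treatment-timing groups. No adherence cut-off is given, no test of the refill ratio is specified, and there is no rule for scoring a participant who stops.

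On stopping, Section 7.4.2.5 states: "Subjects who voluntarily discontinue treatment provided by the study will be advised to continue anti-retroviral treatment with public or private sources". The same section invites these participants to stay on the scheduled follow-up visits. Section 7.4.3.4 requires interruptions and permanent discontinuation to be recorded at each visit.

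The schedules in Section 7.4.1 carry a row for "Pharmacy Refills", marked about every four weeks. The days supplied per script are not stated. Section 6.3.6 has the pharmacist log label information and a date for each bottle.

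For the population model, Section 11.5.4 says that "adherence data (pill count, recall) will be used for analysis".

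**The concern.** The denominator needs two dispensing dates. After the last script there is no second date, so the later days enter neither part of the ratio. The measure registers late refills but need not register stopping.

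That time is not lost to the trial, because participants who stop study drug are invited to stay in follow-up. No section links those visits, or the record of discontinuation, to the ratio. No section says what an interval without a script scores.

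At stake is the adherence part of secondary endpoint 6. The refill ratio is meant to offset the optimism of self-report, and a ratio that leaves out time after stopping can err in the same direction.

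**Working it through.** The documents give no adherence figure, so there is nothing of the plan's own to reproduce. I applied the stated formula directly.

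**Inputs.** The formula is from Section 6.3.8. Refills about every four weeks are from Section 7.4.1. Immediate ART runs 48 weeks, or 48 × 7 = 336 days, and deferred ART 24 weeks (Section 6.3.1.3). Assumption: each script supplies 28 days and the first is at week 0.

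**Ratio on closed intervals** = days supplied by scripts that are followed by another script ÷ (date of last script − date of first script).

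**Supply over follow-up** = days supplied by all scripts ÷ 336.

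On-time refills, then no further collection:

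| Last script (week) | Scripts | Closed-interval ratio | Supply over 48 weeks |
|---|---|---|---|
| 4 | 2 | 28/28 = 100% | 56/336 = 16.7% |
| 12 | 4 | 84/84 = 100% | 112/336 = 33.3% |
| 24 | 7 | 168/168 = 100% | 196/336 = 58.3% |
| 36 | 10 | 252/252 = 100% | 280/336 = 83.3% |

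Cases that do not score 100%:

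- Refills every 35 days, with the last script on day 105: 3 × 28/105 = 80%, against supply of 112/336 = 33.3%.
- One script only: there are no days between scripts, so there is no ratio.
- Last script at week 12, with intervals taken one at a time: weeks 24–36 and 36–48 contain no script and have no value.

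**Fixed-window reading.** If "in approximately 3-month intervals" means 12-week windows with 84 days in each denominator, the participant with a last script at week 12 scores 84/84 = 100%, 28/84 = 33.3%, 0% and 0%.

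**Arm comparison.** The documents give no stopping rates, so these are assumptions to show the range, with on-time refills until stopping.

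- Equal share of stoppers (10%), scripts collected uniform on 1–12 (immediate) or 1–6 (deferred). Mean coverage among stoppers is 6.5/12 = 0.54 or 3.5/6 = 0.58. Uncounted loss is 10% × (1 − 0.54) = 4.6 points against 10% × (1 − 0.58) = 4.2 points, a difference of 0.4.
- The same, but leaving out those who collect every script (1–11 or 1–5): coverage is 6/12 = 0.50 and 3/6 = 0.50, a difference of 0.
- Equal risk r of stopping at each refill after the first. The uncounted share of planned ART days is 1 − [1 − (1 − r)^n]/(n × r), with n = 12 or 6. For r = 1% this is 5.3% against 2.5%. For r = 2% it is 10.3% against 4.9%.

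**The case against.** The strongest reply is that stopping will not go unseen. Discontinuation is recorded at each visit, self-report is collected monthly, viral load is a third measure, and endpoint 6 covers retention as well as adherence. All of this stands and limits the damage. It does not repair the ratio, because nothing links these records to it and no rule says how the three measures combine.

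The second reply is that 3-month intervals may mean fixed windows, in which case stopping shows plainly. That reading is possible, but the formula in the same sentence names days between scripts as its denominator, and the text does not settle the matter.

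The third reply is that the 33% measures study-drug supply, not ART taken. Sections 7.4.2.5 and 10.1 direct participants who stop study drug towards ART from elsewhere. This is correct, and a replacement measure must allow for it.

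A reader might infer more than the documents support:

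- That everyone who stops scores as fully adherent. This holds only for on-time refillers summarised over closed intervals. A late refiller keeps the lower ratio, and a participant with one script has none.
- That the comparison is biased in favour of immediate ART. The size and direction depend on assumed stopping rates, and equal stopping proportions give a difference of 0 to 0.4 points at 10% stopping. The plan specifies no between-arm test of this ratio, and some deferred participants may start before week 24 (Section 4.2).
- That the population model is biased. Section 11.5.4 names pill count and recall, not the refill ratio.
- That early refills will offset gaps. No averaging rule is given, so this cannot be determined.

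**Conclusion.** The concern holds in limited form. As written, the refill ratio leaves time after the last script dropped or undefined, and no other section closes the denominator. Adherence for secondary endpoint 6 can be overstated. With 28-day scripts and on-time refills, a last script at week 12 gives 100% on closed intervals against 33% supply over 48 weeks. The fixed-window reading gives 100%, 33%, 0% and 0%. Two readings this far apart are reason enough to settle the text before analysis.

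The average effect on reported adherence cannot be sized from the documents, which give neither stopping rates nor days per script. The primary viral load comparison in Section 11.5.3 does not use this ratio and is unaffected. The population model is affected only if the ratio is used there.

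**What to change.** Replace the formula in Section 6.3.8 with proportion of days covered, calculated per 12-week block:

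- **Denominator:** all calendar days from ART start to the end of observed follow-up. Censor only at death, study withdrawal or documented ART from another source. Days between the last supply and the censoring date stay in.
- **Numerator:** days with study drug in hand, counted at most once per day so that the proportion cannot exceed 1. Days after the last supply count as uncovered.
- **Protocol-directed holds** (Section 9): exclude them from the denominator or report them separately, so that an ordered interruption is not scored as non-adherence.
- **Comparing arms:** report adherence over the same length of time on ART in each arm.
- **Reconcile Section 11.5.4 with Section 6.3.8.** The first names a pill count and the second describes none. State which measure the model will use.

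This needs wording changes and slightly more analysis work, with no added visits. The dispensing log in Section 6.3.6 already holds dates and label information; confirm that days supplied can be read from it. Reported adherence will probably be somewhat lower.
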